#### 5.2.2.5 Outcomes

Each cohort will allow the description of a number of outcomes.

In the HES cohort, the outcomes described will be: type of surgical reconstruction (OPCS code); duration of index admission; time to first subsequent admission with a pressure-ulcer related diagnosis; rate of subsequent admissions with a pressure-ulcer related diagnosis; repeat surgical reconstruction and type of reconstruction; and mortality.

Although the study does not include an economic evaluation, an important output will be a description of the primary and secondary care resources used in managing severe pressure ulcers. These data would be expected to inform any future study.

In the CPRD cohort, the outcomes described will be: frequencies of specific Read codes; referral to and discharge from community/district nursing team, generating periods of community nursing care and durations; referral to tissue viability services; admission to hospital with a pressure ulcer diagnosis, and duration of admissions related to a pressure ulcer; admission to hospital for surgical reconstruction of a pressure ulcer; and mortality.

Table 2: Read codes to identify referrals and discharges within primary care

Medical code Referral to tiss		Description services		
22485 9N2m.00 Seen by tissue viability nurse				
25762 8HHD.00		Referral to tissue viability nurse specialist		
104199	38C5.00	Tissue viability assessment		
108190	8T0J.00	Referral to tissue viability service		
		, , , , , , , , , , , , , , , , , , ,		
Referral to / dis	charge by c	ommunity nurse		
9988	ZL23.11	Under care of community nurse		
12487	ZLA3.11	Seen by community nurse		
26438	ZL63.11	Referral to community nurse		
85246	9N2y.00	Seen by community nurse for older people		
86017	8HI3.00	Referral to community nurse for older people		
12415	ZLD8.00	Discharge by community nurse		
Referral to / dis	charge by d	istrict nursa		
3529	9NFA.00	District nurse visit		
6535	8H72.00	Refer to district nurse		
11495	ZL63211	Refer to district nurse		
11188	8HW1.00	Referral by district nurse		
32042	03FG.00	District nurse		
36890	9NFH.00	District nurse initial visit		
11243	66S5.00	Shared care: district nurse/GP		
12092	ZL23300	Under care of district nurse		
17845	9N24.00	Seen by district nurse		
18592	9NFJ.00	District nurse follow up		
18968	671A.00	Discussed with district nurse		
	9NFE.00			
40802 63301		First annual visit by district nurse		
	66SA.00 9NNg200	Shared care: practice nurse & district nurse Under care of district nurse		
106669	•			
108211	9NFa.00	Home visit request by district nurse		
18072	13GA.00	District nurse involv. stopped		
36900	ZLD8300	Discharge by district nurse		
105318	8HgP.00	Discharge by district nurse		
Deferrel to / dia	oborgo by n	adiatriat		
Referral to / discharge by podiatrist				
7992	9N2Q.00	Seen by podiatrist		
9647	9NN0.00	Under care of podiatrist		
10090	ZL83.00	Referral to podiatrist		
30691	ZL44211	Under care of hospital podiatrist		
32614	ZL83111	Referral to community podiatrist		
38841	ZL44100	Under care of community-based podiatrist		
40620	ZL44111	Under care of community podiatrist		
40892	ZL83200	Referral to hospital-based podiatrist		
41262	ZL83211	Referral to hospital podiatrist		

42276 47319 56717 94317	ZL83100 ZL44200 9N2P.11 8HVd.00	Referral to community-based podiatrist Under care of hospital-based podiatrist Seen by podiatrist Private referral to podiatrist
43483	ZLDG.00	Discharge by podiatrist
59370	ZLDG200	Discharge by hospital-based podiatrist
59374	ZLDG211	Discharge by hospital
60610	ZLDG111	Discharge by community podiatrist
96639	ZLDG100	Discharge by community-based podiatrist

Table 3: Read codes to identify dressing of ulcer/wound

Medical code	Read code	Description
6654	81H1.00	Dressing of ulcer
15506	7G2E500	Dressing of skin ulcer NEC
22204	Z1B2300	Dressing of skin ulcer
17790	Z1B3.00	Dressing of pressure sore
96	81H00	Dressing of wound
28848	81Hy.00	Other wound dressing
19364	81HZ.00	Wound dressing NOS
110388	8Cy00	Wound dressing requested by community nursing team
101142	8C600	Wound dressing requested by accident and emergency service

#### 5.2.2.6 Sample size considerations

Based on the anonymised HES extracts, HES cohort A should comprise about 120,000 index hospital admissions, including about 220 in which surgical reconstruction operations were carried out and about 3,900 in which surgical debridement without reconstruction was carried out. There are also likely to be about 170 subsequent admissions in which operations were carried out over 2 years of follow-up. Usual care for patients not having surgery will be characterised precisely.

We expect the CPRD cohort to comprise about 10,000 incident pressure ulcers. Severe pressure ulcers in the community are mainly managed conservatively; few are admitted to hospital and CPRD only covers 7% of the English population. These data will be summarised descriptively, Outcome frequencies (healing, infection, referrals to community nursing teams, TVNs and secondary care) will be estimated precisely, given this sample size. We expect to be able to follow very few incident ulcers through to surgical reconstruction.

#### 5.2.2.7 Data management and analyses

HES data will be formatted to identify inpatient admissions for continuous periods of care. The index admission will be the first admission with a severe pressure ulcer diagnosis code.

Patients' age, sex and comorbidities and other diagnoses on admission will be described. (35) Comparisons between hospitalised patients with a severe pressure ulcer who did and did not

have reconstructive surgery will be confounded; the risk of bias from confounding was identified in our preliminary discussions with surgeon members of the team.

Our approach will be as follows:

- a. Identify important confounding domains from the surveys of health professionals (Workstream 1).
- b. Classify important confounding domains according to whether we can / cannot characterise them from variables, or patterns of variables (e.g. comorbidities or activity profiles) in the available HES data.
- c. Summarise descriptively the characteristics of eligible patients on index admission, including variables identified as characterising important confounding domains.
- d. Describe standardised differences between the characteristics of groups of eligible patients; (36, 37) subsequent steps e-i are conditional on point estimates of standardised differences being <0.2 for variables characterising important confounding domains.
- e. Fit multivariable models to estimate the propensity for having reconstructive surgery.
- f. Plot distributions of propensity by groups of patients who did and did not have reconstructive surgery.
- g. Optimise the choice of propensity-adjustment method according to the results of d- f, without reference to the distribution of outcomes in the groups. (38, 39)
- h. Fit regression models, adjusting for propensity.
- i. Interpret the findings of the propensity-adjusted models taking into account information from steps a-e (above).

Details of the propensity-adjusted analyses will be described in a statistical analysis plan. If feasible, we will also explore potential subgroup interactions with reconstructive surgery that may influence outcomes, e.g. in relation to comorbidities, previous hospital admission without surgery.

In the CPRD cohort, patients with incident pressure ulcers will be identified by Read codes. GP data will identify major comorbidities and pressure ulcer management provided. A small number will have hospital admissions, identified through linkage with HES data.

Patients' age, sex and comorbidities on diagnosis of a severe pressure ulcer will be described, together with details of their subsequent care in both primary and secondary care settings. We envisage that the expected, very small number of patients in the cohort having surgical reconstruction will prevent any comparisons with patients not having surgery.

5.2.3 Workstream 3: consensus groups to identify who should have surgical management and when

We will use a formal consensus method to elicit the views of health professionals and patients about which treatments and management strategies are appropriate for whom and when. Currently, we propose to use a method based on the modified nominal group technique. (40-42) The appropriateness of using this method will be reviewed as evidence from workstreams 1 and 2 emerges. We propose to recruit participants to four groups, two each of health professionals and patients. The decision to hold a separate consensus process for professionals and patients/carers is based on previous experience, which showed that it is difficult to bridge the gap relating to content knowledge and use of technical language between professionals and patients to allow a truly equitable contribution from both types of stakeholders. (43)

The consensus process will be structured to yield consensus about the primary output specified in the CB, namely identification of patient groups and interventions requiring primary research to determine effectiveness. The process will construct a set of recommendations about which treatments are appropriate for whom and when.

We will compile statements describing uncertainties about (a) the population that may benefit from an operation, (b) the operations that should be considered and (c) what should constitute usual care (range of treatment and duration before referral for a surgical opinion). These statements will be informed by the updated systematic review, survey responses of the multiple professions managing severe pressure ulcers and phenomenological interviews with patients (Workstream 1) and the findings from the retrospective cohort studies (Workstream 2).

We will provide summaries of the findings of Workstreams 1 and 2 (in suitable language format for patients and carers) and the statements to panel members before consensus meetings. Panel members (up to 12 per panel meeting) will respond to statements in private before the meeting; we envisage that statements will be presented on paper or electronically with supporting information, 9-point Likert scales (1 indicating "completely disagree" and 9 "completely agree") and space for free text comments. Panel members will then attend a face-to-face meeting, discuss in turn anonymised aggregate responses to the first survey for each statement and then independently rate the statement again. Criteria for consensus will be: a median score of response ≥7 and interquartile range (IQR) of 6–9 in support of a statement; a median score of ≤3 and IQR of 1–4 in disagreement with a statement. The outputs of the consensus meetings will be descriptions of statements for which there is consensus among panel members about the populations that may benefit from an operation, the operations that should be considered and what should constitute usual care.

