Secondly, the study will analyse data collected routinely in the NHS over a period of 8 years. The study will describe the care that has been provided in England to patients with severe pressure ulcers, the kinds of patients who have been treated in different ways and examine how care is different in different places. To inform whether surgical treatments should be more widely available, the study will identify patients who were similar when admitted to hospital with a severe pressure ulcer and compare health outcomes (such as going back to hospital and death) among those who did and did not have surgery.

Thirdly, the study will hold meetings with experienced healthcare professionals and patients to review the survey findings and the data analyses. The study will use an established method to reach agreement about which treatments are appropriate and for whom. These steps are vital to ensure relevant future research.

This study will be carried out by an experienced multi-disciplinary team of surgeons, tissue viability nurses, statisticians, researchers and patient representatives. We expect it will take two years to complete. The results will be made publicly available to inform the future care of patients with severe pressure ulcers.

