- Describe in the HES cohort patients with a diagnosis of severe pressure ulcer at the time of hospital admission, their care pathways after admission and frequencies of health outcomes.
- 5. Compare in the HES cohort outcomes in matched groups of patients who were similar on admission and who did/did not have a surgical reconstruction operation.
- 6. Explore in the matched groups subgroup interactions with reconstructive surgery that may influence outcomes, e.g. comorbidities, previous hospital admission without surgery.

[figure not shown]
Workstream 3 is a formal consensus process, separately among health professionals and patients and carers, to make recommendations about which treatments are appropriate for whom and when. The objective of Workstream 3 is to:

7. Seek consensus about which treatments and management strategies are appropriate for whom and when, given findings from workstreams 1 and 2.

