#### 5.2.2.1 HES cohort design and target population

We will request data for index admissions with a severe pressure ulcer (ICD-10 codes L89.2, L89.3, L89.9) or any pressure ulcer (L89.X) during a period of 8 years (01/04/2011-31/03/2019), linked with other HES APC and outpatient episodes and mortality data (to 31/03/2019). The target population for the HES cohort is: patients >=18 years of age in England admitted to hospital, with an ICD-10 diagnosis code for a severe pressure ulcer.

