102230	M270100	Nursing home acquired pressure ulcer
102923	M270300	Hospice acquired pressure ulcer
103207	M270000	Hospital acquired pressure ulcer
103311	38Dr.00	EPUAP (Euro pressure ulc advisry panl) classification system
104552	M270z00	Decubitus ulcer and pressure area NOS
104850	M270400	Stage I decubitus ulcer and pressure area
105150	M270500	Stage II decubitus ulcer
106686	M270600	Stage III decubitus ulcer
106902	M270700	Stage IV decubitus ulcer
108537	M270.14	Decubitus ulcer and pressure area

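### The HES index rule accepts any continuous period of care with a severe ulcer code, while objective 4 and the study summary concern ulcers present when the patient is admitted

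*Protocol*

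**What the plan says.** Two parts of the protocol describe the HES population by the patient's state on arrival. Objective 4 in section 4 is to "Describe in the HES cohort patients with a diagnosis of severe pressure ulcer at the time of hospital admission". The study summary in section 1 describes the surgical comparison as an attempt to "identify patients who were similar when admitted to hospital with a severe pressure ulcer". Objective 5 is to "Compare in the HES cohort outcomes in matched groups of patients who were similar on admission"; that sentence asks for similarity on admission and does not itself say that the ulcer was already there.

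The operating definitions are looser. Section 5.2.2.1 sets the target population as adults in England "admitted to hospital, with an ICD-10 diagnosis code for a severe pressure ulcer". Section 5.2.2.7 says that "HES data will be formatted to identify inpatient admissions for continuous periods of care" and that "The index admission will be the first admission with a severe pressure ulcer diagnosis code". Sections 2.2 and 4 also describe the index admission only as one that includes, or is assigned, such a code.

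Baseline is described in section 5.2.2.7 as comorbidities, diagnoses and characteristics on admission. The details of the propensity analysis are left to a statistical analysis plan. Length of the index admission is among the HES outcomes in section 5.2.2.5.

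**The concern.** A continuous period of care can be long and can contain several episodes. A rule that asks only whether the period carries a severe ulcer code does not distinguish a patient who arrived with a deep ulcer from one who developed it weeks into a stay for another illness. The second patient is outside objective 4, yet is indexed from an admission date on which the ulcer did not exist.

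Three things are at stake. First, the description promised by objective 4 would mix two populations without showing the split. Second, for an ulcer that arises in hospital, the length of the index admission counts days before the ulcer. Third, the comparison of surgery with no surgery could be affected if ulcers acquired in hospital are more common in one group than the other and carry a different prognosis. A related risk is that diagnoses first made later in the same period of care are read as baseline, because the protocol gives no way of telling them from diagnoses present at the start.

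**Working it through.** The plan states no figure on this point to reproduce, so the main check sets the definitions side by side.

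- Section 4, objective 4: severe ulcer diagnosed at the time of admission.
- Section 1: patients alike when admitted with a severe ulcer.
- Section 4, objective 5: groups alike on admission, with no separate statement on when the ulcer arose.
- Section 5.2.2.1: admitted, with a severe ulcer code. No timing.
- Section 5.2.2.7: records joined into continuous periods of care; index is the first admission with a code. No limit by episode, diagnosis position or timing.
- Sections 2.2 and 4, descriptions of the HES cohort: the admission includes or is assigned a code. No timing.

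Taken literally, the last three items admit every patient that objective 4 describes, and also patients whose code arises later in the stay. No section excludes the second group from the HES cohort or reports it separately.

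**How many admissions.** Section 5.2.2.6 expects about 120,000 index admissions, about 220 with reconstruction. The share of ulcers arising in hospital is not given. With an assumed share p, the number outside objective 4 is p × 120,000:

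- p = 10%: 12,000
- p = 30%: 36,000
- p = 50%: 60,000

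Even if all 220 surgical admissions were of this kind, at least 12,000 − 220 = 11,780, 36,000 − 220 = 35,780 or 60,000 − 220 = 59,780 would be non-surgical. In numbers, these admissions would therefore lie almost wholly in the comparator. That says nothing about the share within each group, and bias depends on those shares.

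**Direction of bias.** Let c and t be the shares of hospital-acquired ulcers in the comparator and surgical groups, and let h and a be mortality with ulcers acquired in hospital and ulcers present on admission. If surgery has no effect, crude mortality is a + c(h − a) in the comparator and a + t(h − a) with surgery. The difference, comparator minus surgery, is (c − t)(h − a). None of the four quantities is in the documents. For illustration only, assume a = 15%, h = 30% and c = 40%, so comparator mortality is 15 + 0.40 × 15 = 21%:

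- t = 0%: surgical mortality 15%; crude relative risk 15/21 = 0.71
- t = 40%: surgical mortality 21%; crude relative risk 21/21 = 1.00
- t = 60%: surgical mortality 15 + 0.60 × 15 = 24%; crude relative risk 24/21 = 1.14

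The sign changes with t, and these are unadjusted figures. The documents settle neither size nor direction.

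**The case against.** The strongest reply is that the wide rule is inferred from silence. The protocol nowhere says that a code in any episode qualifies, and joining records into continuous periods is not itself an error. This is fair as far as it goes. But the target population and the index rule are fixed in the protocol; only the propensity details are deferred. Followed as written, these definitions are wider than objective 4.

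A reader might infer that complications arising during the stay will be put into the propensity model as baseline. The text does not support that. Section 5.2.2.7 speaks of diagnoses on admission, and the statistical analysis plan may say how they are dated. Only the risk remains.

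A reader might also infer that the comparator's mortality will be inflated and surgery will look beneficial. That needs an assumed share, assumed mortality rates and few or no hospital-acquired ulcers among surgical patients. It also ignores the planned propensity adjustment and the condition that standardised differences be below 0.2. Nor can one say that the cohort is the wrong one for the future trial: sections 2.1 and 4 say that the trial population is still to be defined. The Read code "Hospital acquired pressure ulcer" in Table 1 belongs to the CPRD cohort; it shows awareness of the distinction and no error in HES.

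Two further objections stand and shape the remedy. A code in the first episode does not prove that the ulcer was present on arrival. A hard filter could also remove surgical patients whose ulcer is first coded in the episode with the operation, which would conflict with the intention in section 2.2 to present everyone managed surgically. Rewording objective 4 would also remove the contradiction, but it would leave the two groups pooled.

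**Conclusion.** The mismatch is real and lies in text that the protocol fixes itself. Objective 4 and the study summary concern patients who have a severe ulcer when admitted; sections 5.2.2.1 and 5.2.2.7 require only that the period of care carries a code. Ulcers that develop during the stay can therefore enter and be indexed before they existed, and the length of the index admission then includes days before the ulcer. For objective 5, the link to an ulcer already present on admission comes from the study summary and not from the objective's own sentence.

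The number affected is unknown: 12,000 to 60,000 admissions under assumed shares of 10% to 50%. The size and direction of bias in the surgical comparison cannot be derived from the documents. This should be put right before the data are analysed, but it does not show that the comparison will mislead.

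**What to change.** Reconcile sections 1, 4, 5.2.2.1 and 5.2.2.7 as follows.

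- Flag each index admission by whether L89.2, L89.3 or L89.9 first appears in the first or in a later episode of the continuous period of care.
- For objective 4, report the two groups separately.
- For objectives 5 and 6, run the comparison restricted to first-episode codes and again with codes from any episode. State which is primary before outcomes are seen.
- Take baseline diagnoses from the first episode and from earlier admissions.

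The cost is one derived variable and one repeated analysis, provided the extract keeps episode order. The downside is that the first-episode code is an imperfect proxy for an ulcer present on admission: late coding will move some genuine cases out of the restricted analysis, and may do so unequally by group. With only about 220 surgical admissions, even a modest loss matters, so report the number moved in each group. The any-episode analysis retains every surgical case.

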## 6. Study management

The study will be managed by the Bristol Trials Centre, Clinical Trials and Evaluation Unit (CTEU). The CTEU is an UK Clinical Research Collaboration registered Clinical Trials Unit. The CTEU will prepare all the study documentation, carry out administrative tasks, carry out study analyses in collaboration with other investigators and assist in preparation of study outputs.

## 6.1 Day-to-day management

The study will be managed by a study management group (SMG). The SMG will convene every 6 months, face-to-face or by teleconference, to review progress; there will also be monthly teleconference updates. The SMG includes the full range of expertise that the study team may need to draw on. The SMG will be chaired by the Chief Investigator (CI) and will include all members of the named research team.

## 6.2 Study Steering Committee, and Data Monitoring and Safety Committee

In agreement with the study funder, there will not be a Study Steering Committee or Data Monitoring and Safety Committee convened for this study. The study will be overseen by the coapplicants, who will form the SMG. There is no safety issue, since the study comprises retrospective cohort studies and consensus groups.

